### **4.2 Selection of study population**

Male and female adult ( $\geq 18$  years old) patients who are diagnosed with HLH and meet the inclusion criteria.

### **4.3 Method of treatment assignment and randomization**

This is an observational study (not randomized). Please see details on study population section 4.2

## **5 Sequence of planned analysis**

### **5.1 Interim analyses**

There was no planned interim analysis for this observational study.

### **5.2 Analyses and reporting**

All final analyses identified in the protocol and in this SAP will be performed only after the database lock. A data review will be held prior to database lock. The SAP will be finalized, locked and signed prior to database lock.

Any post-hoc analyses included in the study synopsis which were not identified in this SAP, will be clearly identified as such in the relevant report section.

## **6 Sample size determination**

No formal sample size was calculated for this observational study.

The protocol stated a a minimum of 14 (maximum of 40) adult patients with HLH will be studied, including a minimum of 7 patients with HLH of unknown origin (i.e. in whom a trigger for HLH cannot be identified).

A total of 14 patients where included in the study, 6 of whom had an unknown HLH trigger. Four patients diagnosed with a malignancy where included in the study.

## **7 Analysis populations**

The All enrolled set will be used in the statistical analyses as no study drug was administered.

### **7.1 All enrolled set**

All subjects who signed an informed consent.

## 8 General issues for statistical analysis

No statistical tests will be presented. Only exploratory descriptive statistics will be displayed as described below:

Continuous data will be summarized using descriptive statistics: n, mean, standard deviation (SD), median, minimum, 1st quartile, 3rd quartile and maximum, unless otherwise indicated. Minimum and maximum will be presented to the same number of decimal places as the raw data and mean, standard deviation and median will be presented to one more decimal place than the raw data.

Categorical data will be summarized using counts and percentages. Percentages will be suppressed when the count is zero, however the category will still be displayed. The denominator for all percentages will be the number of patients within the group for the population of interest, unless otherwise indicated. Percentages will be presented to one decimal place.

All data will be listed in individual patient data listings.

Four patients diagnosed with a malignancy (and hence classified as M-HLH) were included in the study, according to the protocol these patients are to be analysed separately. All data presentations will be split by M-HLH and A-HLH (all patients without malignancies).

Statistical analyses will be performed using SAS software Version 9.4 or later (SAS Institute Inc, Cary, North Carolina, United States).

### 8.1 Handling of missing data and outliers

No imputation of missing data will be performed.

### 8.2 Multicenter studies

Not applicable. This observational study was conducted in one site.

### 8.3 Multiple comparisons and multiplicity

No comparison and multiplicity adjustment will be performed, only descriptive statistics.

### 8.4 Derived and computed variables

#### 8.4.1 Age

Age at informed consent (years) will be calculated as:

$$\text{Age (years)} = \frac{\text{Date of informed consent} - \text{Date of birth}}{365.25}$$

Age at HLH diagnosis (years) will be calculated as:

$$\text{Age at HLH diag. (years)} = \frac{\text{Date of HLH diagnosis} - \text{Date of birth}}{365.25}$$

Ages will be rounded to the closest whole year for presentation in the summary tables and listings.

#### 8.4.2 LLOQ and ULOQ

Values reported as below the lower limit of quantification (LLOQ) will be replaced by LLOQ/2 and values above upper limit of quantification (ULOQ) will be replaced by ULOQ prior to the statistical analyses.

### 9 Patient disposition

Not applicable, all patients who signed an ICF will be enrolled in the study. No study treatment is given.

## 10 Demographics and baseline characteristics

### 10.1 Demographics

Demographic characteristics will be summarized for the All enrolled set and split by A-HLH and M-HLH groups:

- Age (years) at ICF
- Sex: Male, Female
- Race
- Weight (kg) at ICF
- Height (cm) at ICF

Demographic data will also be listed.

### 10.2 Medical History

Medical History characteristics will be summarized for the All enrolled set and split by A-HLH and M-HLH groups and will include:

- HLH Diagnosis
  - Age at HLH diagnosis (years)
  - Molecular diagnosis relevant for HLH: Yes, No, Not Tested
  - Mutation (if molecular diagnosis): List as entered

- CNS involvement
  - Bone marrow biopsy
    - Evidence of hemophagocytosis
      - List additional info if available
  - Other biopsy
    - Evidence of hemophagocytosis
      - List additional info if available
- Known underlying immunodeficiency
- Has HLH been diagnosed in any family member
- Functional tests at diagnosis
  - Decreased or absent NK cell cytotoxicity
  - Degranulation assay
  - Perforin expression
  - List comments if available
- HLH trigger detected: Yes, No, Not Tested
  - Age at diagnosis of triggering disease
    - Infection Yes/No
      - Type, pathogen and viral load will be listed if available
    - Rheumatologic disease
      - Type listed if available
    - Malignancy
      - Type and induction listed if available
    - Other HLH trigger
      - Details listed if available
- Other relevant diagnosis at sample procurement
- HLH criteria fulfilled
  - Fever
  - Splenomegaly
  - Cytopenias
  - Hypertriglyceridemia and/or hypofibrinogenemia
  - Hemophagocytosis in bone marrow
  - Ferritin (>500 ug/L)
  - sIL-2R (>2,400 U/mL)
  - Low or absent NK cell activity

Medical History Characteristics data will also be listed.

## 11 HLH outcome

HLH outcome will be summarized for the All enrolled set and split by A-HLH and M-HLH groups and will include:

- HLH resolved (Yes/no)

- HLH reactivated (Yes/no)
- Has HSCT been performed (Yes/no)
- Is patient alive (Yes/no)

## 12 Prior and concomitant medication

### 12.1 HLH therapy

- Treatments received (Steroids, etoposide,IVIg, CaNeur Inhibitors, Other)

List name of drug, dose frequency etc if available. Entered as free text in CRF and will not be coded.

[figure not shown]

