### 3.2.2 Inflammatory biomarkers- correlation

The degree of correlations between inflammatory markers and between selected inflammatory markers and markers of disease activity (lab assessments) will be investigated.

The inflammatory biomarkers are as listed in section 3.2.1 and the other laboratory assessments as defined in the protocol are listed below

- Albumin
- AST, ALT, Alkaline Phosphatase
- Basophils
- $\beta$ 2-microglobulin
- Total and conjugated Bilirubin
- BUN, serum creatinine
- CRP
- D-dimers
- Hemoglobin, Hematocrit, Red blood cells, white blood cells and differential count, platelets
- Fasting triglycerides
- Ferritin
- Fibrinogen
- Lactate dehydrogenase
- NK cell activity
- PT and aPTT
- Serum IgG
- Sodium

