### **13.2 Inflammatory biomarkers - correlations**

The degree of correlations between inflammatory markers and between inflammatory markers and laboratory assessments (potential markers of disease activity) will be assessed.

The correlations to be performed are:

1. All inflammatory biomarkers vs. all other inflammatory biomarkers as listed in section 3.2.1
2. Biomarkers relevant for emapalumab (i.e. CXCL9, CXCL10, IFN $\gamma$  and sIL2R $\alpha$ ) vs. all laboratory assessments as listed in section 3.2.2

The correlations will be evaluated by plotting biomarker scores i.e., CXCL9 vs. CXCL10 (for all combinations) in scatter plots. The biomarker value closest to the date of HLH diagnosis will be used if more than one sample available. A-HLH and M-HLH patients will be shown in the plots with different colours or symbols.

Data will be investigated to confirm normal or log-normal distribution of the parameters. If normal, the actual values will be plotted. If not normal, log-transformed values will be plotted.

The correlated samples should be within a time frame of three days.

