## 14.2 Laboratory data

A subset of the laboratory data collected will be displayed in scatter plots the same way as the biomarker data described in section 13.1. The lab data to be plotted are:

- AST, ALT, Alkaline Phosphatase
- Total and conjugated Bilirubin
- CRP
- D-dimers
- white blood cells and differential count, platelets
- Ferritin
- Fibrinogen
- Lactate dehydrogenase

The value closest to the date of HLH diagnosis (value must be after HLH diagnosis) will be used if more than one sample is available.

Laboratory data will be summarized by A-HLH and M-HLH groups using descriptive statistics.

All laboratory data will be listed by patient.

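### SAP 13.2 plots serum IgG as a potential disease-activity marker, but no rule handles IgG values drawn after IVIg, a listed HLH therapy that is itself IgG

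*SAP*

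**What the plan says.** SAP 3.2.2 includes serum IgG in its list of laboratory assessments and gives the list its role: "markers of disease activity (lab assessments) will be investigated". SAP 13.2 is more cautious and speaks of "laboratory assessments (potential markers of disease activity) will be assessed". Item 2 of that section sets CXCL9, CXCL10, IFN-gamma and sIL2R-alpha "vs. all laboratory assessments as listed in section 3.2.2", so serum IgG is plotted without any condition. The method is graphical: "The correlations will be evaluated by plotting biomarker scores".

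SAP 12.1 gives the categories of HLH therapy: "Treatments received (Steroids, etoposide,IVIg, CaNeur Inhibitors, Other". Of the detail behind them it says: "Entered as free text in CRF and will not be coded".

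Samples are chosen by date only. SAP 13.2 states: "The biomarker value closest to the date of HLH diagnosis will be used if more than one sample available". It also asks that paired samples lie within three days of each other. SAP 14.2 adds for laboratory data: "value must be after HLH diagnosis) will be used if more than one sample is available". Neither section mentions therapy, and the plot symbols in 13.2 separate only A-HLH from M-HLH.

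**The concern.** The usual worry about treatment in a biomarker study is that it changes the disease, so that samples taken at different times reflect different disease states. Pairing samples closely helps with that. The problem here is different. Intravenous immunoglobulin consists of IgG, so after an infusion the assay measures the patient's own IgG plus the product. A biomarker and an IgG value from the same sample carry the problem in full, and the three-day window does nothing for it.

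At stake is the reading of the IgG plots under the second study objective, the relation between inflammatory markers and disease activity. There are at most 14 patients (10 A-HLH and 4 M-HLH), so a few such points can shape what a plot appears to show. SAP section 2 says these exploratory analyses could be used in regulatory submissions or manuscripts.

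**Working it through.** **1. Can a selected IgG value follow IVIg?** Yes, on the text.

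- The Protocol background says treatment should start promptly once HLH is suspected. The Protocol's Study Design and Procedures collects treatment given before, or ongoing at, HLH onset.
- SAP 13.2 selects the biomarker value by closeness to diagnosis, and SAP 14.2 requires the laboratory value to come after diagnosis.
- No section excludes, flags or stratifies values by IVIg.
- On the other side, the Protocol parameter list places this panel at the time of diagnosis and asks for IgG only if available. Some selected values may therefore precede any IVIg, and some patients may have no IgG value.

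**2. How many plots?** One for each marker in item 2: CXCL9, CXCL10, IFN-gamma and sIL2R-alpha, which makes 4. SAP 3.2.1 lists two IFN-gamma assays (V-PLEX and total). If both are used, the count is 5.

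**3. How many patients?** Fourteen were included, 4 with malignancy, so 14 − 4 = 10 A-HLH. The documents give no IVIg counts or dates. The number affected lies anywhere from 0 to 14.

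**4. Size of the effect.** The plan gives no figure to reproduce, so what follows is an assumed illustration. Take 10 patients and a true correlation of 0.6 between marker and the patient's own IgG. Let k of the 10 have IgG raised by d standard deviations through IVIg, and leave the marker unchanged. With p = k/10, the large-sample correlation is

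r' = 0.6 / √(1 + d²·p·(1 − p))

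- k = 2, d = 1: 0.6 / √(1 + 1 × 0.16) = 0.6 / √1.16 = 0.56
- k = 3, d = 2: 0.6 / √(1 + 4 × 0.21) = 0.6 / √1.84 = 0.44
- k = 5, d = 3: 0.6 / √(1 + 9 × 0.25) = 0.6 / √3.25 = 0.33

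The average sample correlation at n = 10 is a little lower. By simulation:

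| Scenario | Mean r at n = 10 |
|---|---|
| No IVIg | 0.58 |
| k = 2, d = 1 | 0.53 |
| k = 3, d = 2 | about 0.4 |
| k = 5, d = 3 | 0.29 |

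The loss runs from 0.58 − 0.53 = 0.05 to 0.58 − 0.29 = 0.29. Without IVIg, the central 95% of simulated correlations already spans about 0 to 0.90.

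**5. Can the infusion alone create a relation?** Not on average. With a true correlation of 0 and only IgG shifted, the simulated mean is 0.00 in all three scenarios. If the marker is also assumed 1 SD lower in the treated patients, the means become about −0.15, −0.30 and −0.39. That result comes from the second assumption, which is ordinary confounding by treatment.

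**The case against.** The case against is substantial on size.

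- **Number affected.** The documents give no IVIg use at all, so it may be zero. Selecting values close to diagnosis limits exposure to IVIg, although it does not rule it out. This stands.
- **No coefficient is promised.** SAP 13.2 evaluates correlations by plotting, and SAP section 8 says no statistical tests will be presented. The consequence is a misleading point on a plot, not a wrong error rate. This stands, and the correlations above only indicate how much a plot could be blurred.
- **Noise.** In the mildest scenario the loss of 0.05 is far inside sampling variation at n = 10. This stands. The loss of 0.29 assumes that half the patients have values after IVIg with a 3 SD shift, which no document figure supports.
- **Listings.** Therapy and laboratory data are both listed by patient, so a reader could check IgG against IVIg by hand. This is partial mitigation, since the plots themselves carry no warning.

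Three stronger readings are tempting. A reader might infer that the IgG plots are invalid as a whole; only points drawn after IVIg are uninterpretable, and there may be none. A reader might infer that infused IgG by itself produces a false negative correlation; step 5 of the working shows it does not. A reader might take the IgG summary in SAP 14.2 as certainly affected. IgG is not in that section's plotted subset, and the sentence on summarising laboratory data does not say whether it covers the subset or all laboratory data.

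None of this answers the central point: IgG is plotted as a possible activity marker, IVIg is an expected therapy, and no rule connects the two.

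**Conclusion.** The point holds as a minor gap in the analysis rules. As written, the SAP can plot infused product as though it were disease activity, in four IgG plots or in five if both IFN-gamma assays are used. Affected points cannot be interpreted for the second objective, however closely the samples are paired.

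The number of such points is unknown and may be zero. The direct effect is attenuation of a real relation: in the illustration, from a mean of 0.58 to between 0.53 and 0.29. This rests on assumed values for the true correlation, the number treated and the IgG shift. The documents do not support a claim that the IgG plots as a whole are invalid or that a spurious relation is to be expected. The latter would arise only if treated patients also differed in the marker.

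**What to change.** Add a rule to SAP 13.2 item 2, and to 14.2 if IgG is summarised there:

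- Using the recorded HLH therapy, classify each selected serum IgG value as drawn before any recorded IVIg (including patients with none recorded), after IVIg, or of unknown order.
- Base the interpretation of the IgG plots on the first category.
- Show values after IVIg, and values of unknown order, with distinct symbols.
- Leave values known to follow IVIg out of any IgG summary.
- Report the number in each category.

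Marking is better than dropping every value of unknown order. Therapy detail is uncoded free text, given where available, so missing dates alone could remove valid values.

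The cost is a short SAP addition and a manual review of therapy entries for at most 14 patients. The downside is fewer interpretable IgG points. No change to data collection or patient care is involved.

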### 12.2 Concomitant medications (other than for HLH)

Concomitant medication at the time of sample procurement are collected as free text and will not be coded and summarized, only listed as entered in the DCT (Data Collection Tool).

## 13 Endpoint analyses

### 13.1 Inflammatory biomarkers

The inflammatory biomarkers as listed in section 3.2.1 will be displayed in scatter plots and split by A-HLH and M-HLH groups as in the below example.

If several samples available the biomarker value closest to the date of HLH diagnosis (value must be after HLH diagnosis) will be used.

Biomarker data will be summarized for all patients by A-HLH and M-HLH groups using descriptive statistics.

### **13.2 Inflammatory biomarkers - correlations**

The degree of correlations between inflammatory markers and between inflammatory markers and laboratory assessments (potential markers of disease activity) will be assessed.

The correlations to be performed are:

1. All inflammatory biomarkers vs. all other inflammatory biomarkers as listed in section 3.2.1
2. Biomarkers relevant for emapalumab (i.e. CXCL9, CXCL10, IFN $\gamma$  and sIL2R $\alpha$ ) vs. all laboratory assessments as listed in section 3.2.2

The correlations will be evaluated by plotting biomarker scores i.e., CXCL9 vs. CXCL10 (for all combinations) in scatter plots. The biomarker value closest to the date of HLH diagnosis will be used if more than one sample available. A-HLH and M-HLH patients will be shown in the plots with different colours or symbols.

Data will be investigated to confirm normal or log-normal distribution of the parameters. If normal, the actual values will be plotted. If not normal, log-transformed values will be plotted.

The correlated samples should be within a time frame of three days.

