Data collection may be performed retrospectively if sufficient clinical information is available to allow for a meaningful interpretation of the biomarker results.

For biomarker analysis, a maximum of 5 ml of whole blood will be required per time point. Details on sample processing and shipment will be described in a separate brief laboratory manual provided to the site. Whenever possible, serum (and not plasma) should be obtained for shipment, as this is the preferred matrix for the biomarker analysis.

Relevant clinical information gathered by the treating physician will be collected in a data collection form. This will include information on the clinical presentation of HLH, the assessments performed to characterize the secondary form, in particular those for identification of the potential HLH trigger, the date of onset of the background disease (if any) in relation to HLH manifestations, treatment regimen prior to and/or ongoing at the time of HLH onset, clinical and laboratory parameters relevant to HLH, specific HLH therapy with best response to the therapy, other concomitant medications, patient follow-up and disposition, stem cell transplant status, duration of response, and survival. As appropriate, collection of serum samples for biomarker analysis and relevant information should occur at HLH diagnosis, and at regular time intervals during the treatment course (not more than once a week) up to resolution of HLH.

If patients present CNS involvement and lumbar puncture is being performed for diagnostic or therapeutic purposes, a CSF sample will be collected, if possible, for biomarker assessment, in particular CXCL9 and CXCL10.

If feasible and consistent with the standard clinical practice at the site, genetic characterization will be performed. A specific consent for genetic testing must be given by the patient. Genetic samples

CONFIDENTIAL

may also be collected from existing bank of samples (frozen whole blood in EDTA or frozen extracted DNA), if the patient's consent has been previously obtained.

Medical history, in particular all available information on search conducted for the identification of the potential HLH trigger needs to be collected.

Study Duration: This study will gather information on adult HLH patients at diagnosis and, as available, during treatment of the disease up to HLH resolution, and will last until completion of the planned recruitment.

Parameters:

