- 1. Laboratory parameters**, at the time of HLH diagnosis, to be assessed at the site laboratory, such as:
 - Hemoglobin, Hematocrit, red blood cells, white blood cells and differential count, platelets
 - Fibrinogen
 - Ferritin
 - Fasting triglycerides
 - AST, ALT, Alkaline Phosphatase
 - BUN, serum creatinine
 - Albumin
 - Sodium (if available)
 - Beta2 microglobulin (if available)
 - Serum IgG levels (if available)
 - Lactate dehydrogenase
 - Total and conjugated Bilirubin
 - D-dimers
 - PT, aPTT
 - CRP
 - Functional tests, such as perforin expression and NK-cell activity (if performed)

Results of additional tests performed for the patient's follow-up at regular time intervals during the treatment course (not more than once a week) up to resolution of HLH will be recorded, as available.

CONFIDENTIAL

2. Other relevant parameters, at the time of sample collection, in particular body temperature, spleen and liver size (if available), findings in bone marrow biopsy.

3. Inflammatory markers of disease activity. The following assessments will include but not be limited to:

- IFN γ
- sCD25
- IL-1 β , IL-6, IL-10, IL-17 IL-18
- TNF α
- CXCL9, CXCL10, CXCL11
- sCD163 and neopterin

These tests will be performed at Novimmune Bioanalytical Laboratory and results will be made available to the patient's treating physician and to the patient.

4. Medical history, in particular any available additional information on the background disease considered to be the potential trigger of HLH, e.g.:

- Infections (including viral load, bacterial and/or fungal search)
- Rheumatologic diseases

Statistical Analysis:

All analyses are exploratory. Statistical analyses of the data collected in this study will be focused on providing tabular and graphical summaries of the levels of inflammatory markers and of the clinical features of the disease both at diagnosis and during the course of treatment. The degree of correlation between inflammatory markers, and between inflammatory markers and the severity of clinical manifestations, response to therapy, and survival of the patients will be assessed. Analyses may also be performed to study these relationships in various subgroups of patients, depending on the demographic, genetic and clinical characteristics observed (notably, HLH of unknown origin representing a specific subgroup of interest).

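### SAP 13.2 promises the degree of correlation but plans only scatter plots, so objective 2 gets no stated strength, precision or number of complete pairs

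*SAP*

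**What the plan says.** The Statistical Analysis part of the protocol synopsis commits to assessing "The degree of correlation between inflammatory markers", and also between markers and clinical severity, response to therapy and survival. SAP 3.2.2 carries part of this forward: "The degree of correlations between inflammatory markers and between selected inflammatory markers and markers of disease activity (lab assessments) will be investigated". SAP 13.2 again says the degree will be assessed and lists two sets of pairs: every marker against every other marker, and the emapalumab-relevant markers (CXCL9, CXCL10, IFNγ, sIL2Rα) against every laboratory item in 3.2.2.

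The method follows in one sentence of 13.2: "The correlations will be evaluated by plotting biomarker scores". A-HLH and M-HLH patients are to be distinguished by colour or symbol. The normality check decides only whether raw or log values are plotted. On pairing, "The correlated samples should be within a time frame of three days".

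SAP 8 rules out statistical tests and adds: "Only exploratory descriptive statistics will be displayed as described below". What it then describes is n, mean, SD, median, quartiles and range for one variable at a time. SAP 8.1 states: "No imputation of missing data will be performed". SAP 15, on changes from the protocol, mentions only the three unreported markers and the dropped genetic analysis.

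**The concern.** Degree is a quantity, and the planned output does not state one. Objective 2 is to assess the relationship between the cytokines and disease activity, and 13.2 is the only place where the SAP relates the two. The outcomes in SAP 11 are tabulated but never set against markers. Any later statement that, say, CXCL9 correlated with ferritin would therefore rest on visual judgement or on a statistic chosen after the data were seen. SAP 2 says these analyses could enter regulatory submissions or manuscripts.

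The number of complete pairs matters too, because the n in SAP 8 belongs to a single variable. Marker-by-marker pairs may mostly come from one blood draw, since the protocol sets a single blood volume per time point for biomarker analysis; it does not say that every marker was assayed on each sample. Marker-by-laboratory pairs can vary more. They depend on the three-day window and are not imputed, and the protocol collects four of the items in SAP 3.2.2 only if available or performed: sodium, beta2-microglobulin, serum IgG and NK-cell activity.

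**Working it through.** The documents give no correlation, precision or calculated sample size, so there is no figure of the plan's own to reproduce. The working counts what is planned and shows what the plots would leave unstated.

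**Inputs**
- Markers in SAP 3.2.1: 11.
- Laboratory items in SAP 3.2.2: 26 if each named test counts once and basophils are the only differential item; 30 if the differential adds four further cell types (assumed).
- Markers set against laboratory items: 4, or 5 if both IFNγ assays in 3.2.1 are used (an assumption about how 13.2 is read).
- Patients (SAP 6): 14, of whom 4 have malignancy, so A-HLH has at most 14 - 4 = 10.

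**Number of pairs**
- Marker by marker: C(11,2) = 55.
- Marker by laboratory item: 4 × 26 = 104 up to 5 × 30 = 150.
- Total: 55 + 104 = 159 up to 55 + 150 = 205.
- If NK-cell activity is recorded only as yes/no and drops out: 55 + 4 × 25 = 155 up to 55 + 5 × 29 = 200.
- Pairs involving the four optional laboratory items: 4 × 4 = 16 up to 5 × 4 = 20.

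**Precision in A-HLH.** The Bonett-Wright 95% interval for Spearman's rho is tanh[atanh(rho) ± 1.96 × sqrt((1 + rho²/2)/(n - 3))]. Take an assumed observed rho of 0.6. At n = 10, atanh(0.6) = 0.693 and the half-width is 1.96 × sqrt(1.18/7) = 0.805, so the limits are tanh(-0.112) = -0.11 and tanh(1.498) = 0.90. The counts below 10 are assumed.

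| Complete pairs | 95% interval at rho = 0.6 |
|---|---|
| 10 | -0.11 to 0.90 |
| 8 | -0.25 to 0.93 |
| 6 | -0.49 to 0.96 |
| 4 | -0.89 to 0.99 |

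**What chance alone produces.** From the exact permutation distribution without ties, unrelated variables give |rho| ≥ 0.5 with probability 0.144 at n = 10, 0.216 at n = 8 and 0.297 at n = 6. With 10 complete pairs throughout and no true association, the expected number is 0.144 × 155 = 22.3 to 0.144 × 205 = 29.5. These expectations do not require the pairs to be independent of each other.

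**Choice of a minimum count.** The interval cannot be computed when |rho| = 1. Under no association that happens with probability 8.3% at n = 4, 1.7% at n = 5 and 0.28% at n = 6, which supports a minimum of about 6.

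**Does the interval hold with tied values?** SAP 8.4.2 replaces values below the quantification limit with LLOQ/2, which creates ties. In simulations with 0%, 30% or 50% of one marker tied (assumed shares), underlying correlations from 0 to 0.9 and 20,000 runs each, coverage where the interval was estimable was 95.3% to 97.8% at n = 10, 96.0% to 98.2% at n = 8 and 96.7% to 99.1% at n = 6. The method holds and is conservative at 6.

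**The case against.** The best defence is that the protocol calls all analyses exploratory and centres them on tables and graphs, and SAP 8 excludes tests. For so few patients, a plot of every pair with the groups marked is a legitimate display. Each plotted point is one complete pair, so a reader can count them, and the patient listings would let anyone calculate a coefficient. On the figures above, a table would not separate chance from real associations. A 95% interval also invites comparison with zero: with no true association and n = 10, it excludes zero in about 3.5% of pairs, or 0.035 × 155 = 5 to 0.035 × 205 = 7 pairs. A shorter repair would be to print n and rho on each plot, or to reword the commitment as graphical exploration and record that in SAP 15.

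Part of this stands. The over-reading risk is real, and the pair count is not wholly hidden, although points tied at LLOQ/2 can overlap and no n is printed. The rest does not answer the point. A coefficient is descriptive and an interval is estimation, so the bar on tests excludes neither. Small n is a reason to state the uncertainty, because ten points can look persuasive. Rewording would remove the inconsistency but leave objective 2 without a measure. The protocol's promised correlations with clinical severity, response and survival, which 13.2 also omits, are a separate gap.

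**Conclusion.** The concern holds. Three statements promise the degree of correlation, the plan delivers only plots, and SAP 15 does not record the reduction. Between 155 and 205 relationships would be reported with no stated strength, precision or pair count, in a group of at most 10 patients where a rho of 0.6 is compatible with anything from -0.11 to 0.90.

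The range of pairs depends on how the differential count, the two IFNγ assays and NK-cell activity are treated. The intervals depend on the assumed rho of 0.6 and, below 10, on assumed pair counts. The mismatch between promise and method depends on none of these. The change should be made, but the omission invalidates no planned result.

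**What to change.** Keep the scatter plots. Add one paragraph to SAP 13.2 and one descriptive table, for A-HLH only:

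- For each pair, give the number of complete pairs and Spearman's rho with a 95% interval by a named method, for example Bonett-Wright.
- Set a minimum number of complete pairs in advance, for example 6; below it, show only n and the plot.
- Show the interval as not estimable when |rho| = 1, and rho as not estimable when all values of one variable are tied.
- Omit rho for any laboratory item recorded only as yes/no, such as NK-cell activity if that is how it was entered.
- Leave the 4 M-HLH patients as plotted symbols with no coefficient.
- State the number of pairs examined, that the results are hypothesis-generating and that the intervals are not to be read as tests. Report no p-values.

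The cost is that paragraph and a table of up to 205 rows, with no new data. The downside is that many small-sample coefficients could be over-read. The minimum count, the intervals and the stated number of pairs limit that risk without removing it.
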